The rationale for the use in prevention of products useful for the treatment of pressure injuries is also described in the 2013 systematic review (Moore 2013). The incidence of PD is probably reduced through the ability of foam dressings to redistribute mechanical forces. The Guidelines of the European and United States National Pressure Ulcer Advisory Panels (EPUAP and NPUAP) also suggest that the use of foam dressings may protect parts of the body at risk of stretch injuries. The market offers different types of advanced dressings compared to the material they are made of (hydrocolloids, polyurethane foams), their thickness (single or multi-layer) and their dimensions.

Various in vitro comparative studies are available where the different abilities of the main brands of dressings are compared with the pressure redistribution (Call 2015; Matsuzaki 2015; Miller 2015), liquid management (Young 2007) and shear forces (Levy 20015 and Levy 20016) which are the main causative factors of PD development (NPUAP 2014). In these in vitro studies the material that seems to be most effective is polyurethane foam (Matsuzaki 2015; Miller 2015), especially multilayer (Black 2015).

Two systematic reviews published in 2013 and 2014 then evaluated the efficacy on patients of using advanced multi-layer polyurethane dressings in prevention to reduce the incidence of pressure injuries (Clark 2014; Moore 2013). The results of both systematic reviews, although in favor of the use of dressings, are considered by the authors to be inconclusive due to the weakness of the study design found and therefore the high risk of bias. Both reviews concluded by soliciting the production of methodologically more rigorous clinical studies (Clark 2014; Moore 2013). Recently, some trials have been published which confirm the preventive efficacy of polyurethane multilayer foams (Santamaria 2015; Kalowes 2016; Forni 2018; Santamaria 2018) but the populations investigated are very specific, limiting the generalizability of results.

AIM

The aim of the present study was to assess whether the application of a multilayered dressing made of hydrocellular polyurethane foam conformed to the sacral area (MSP) in addition to standard preventive care reduces the rate of pressure ulcer (PU) and their severity in population at risck admitted in acute care Hospital.

Study endpoint

Primary Endpoint

Incidence of PD to the sacrum of any category detected during the first 7 days of hospitalization.

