The 7-day cut off derives from the data in the literature with respect to the average times of onset of the lesions (4th day in the medical field, 5° in the surgical field and 3° in the intensive care unit) with standard deviations that allow to affirm that after 7 days in the acute patients the PD event is extremely rare (Palese 2017; Chiari 2017; Santamaria 2015). PD is defined as a damage to the skin and underlying tissues due to pressure, stretching or friction or a combination of these factors (NPUAP 2014). The incidence of PD is represented by the PD who develop during hospitalization and are not present when the patient is admitted. The injuries will be classified according to the classification defined by the guideline prepared by NPUAP 2014. (attachment).

Secondary Endpoints:

- Incidence of PD to the sacrum category ≥ II ° according to the NPUAP scale
- Skin irritation / damage due to adhesive dressing
- Day of onset of the PD
- Number of dressings used
- Number of patients who stop treatment due to discomfort caused by the dressing (withdrawal)

Other study variables / data collected

- Gender
- Age

- Origin of the patient: first aid, another ward or facility, Short Observation (OBI), Home
- Pregressed (healed) PD to the sacred
- Patient risk level measured with the Braden scale (Pancorbo-Hidalgo PL 2006)
- Days in the study
- Use of the diaper
- Use of the bladder catheter
- Use of anti-decubitus surface (static, preventive dynamics, curative dynamics and air release)
- Daily presence of the caregiver (presence at least during a meal, never, always)

Study Population

Inclusion Criteria:

- Patients at risk of developing PD measured with the Braden scale (Braden \leq 16) with intact sacral skin and / or with signs of healing from previous sacral lesions.
- Patients or legal guardians who consent to the study
- Adult patients
- . Male and female gender
- Expected hospital stay and / or life expectancy > 72 hours
- Patients hospitalized for no more than 24 hours

Exclusion criteria:

- Patients with known allergy to the products under study or with dermatological pathologies that prevent the use of topical products
- Patient with, upon entering the ward, advanced preventive dressing in the sacral region

Design

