At the Research Center for Health Professions of the Rizzoli Orthopedic Institute in Bologna (coordinating center), using the site: www.randomization.com, a randomization list will be generated in blocks of 10. A sequence of opaque envelopes will be prepared with outside a progressive number. Inside the envelope a label will be placed that will contain the words "yes" or "no", according to the sequence indicated by the generated list.

The envelopes will always be sealed at the Research Center and the list kept under lock and key. The envelopes will be placed in a dedicated box and delivered to the nursing research manager of the hospitals involved in the study. In each ward/area a reference nurse will be identified and 40 envelopes delivered.

Statistical analysis

The analysis of the results will be carried out for Intention to Treat.

All continuous data will be expressed in terms of average and standard deviation. One Way ANOVA will be used to evaluate the differences between the averages of the experimental and comparison group. If the Levene test for homogeneity of variance were significant (p <0.05), the Mann Whitney test will be used. For all dichotomous variables the incidence, relative risk, relative risk reduction and number needed to treat will be calculated. The exact

Fisher test will be used to evaluate the differences between the incidences of different outcomes between the experimental group and the control group.

Subgroup analysis:

- by area of belonging (medical, surgical or intensive)
- by risk level according to the Braden classification: Severe (total score 9); High Risk (10-12) Moderate Risk (13-14); low Risk (15-16). (Pancorbo-Hidalgo PL 2006)
- by origin (domicile vs. other settings)

For all tests, a p <0.05 will be considered significant.

The statistical analysis will be done using the "Statistical Package for the Social Sciences" (SPSS) software version 15.0 (SPSS Inc., Chicago, USA)

Possible deviations from the protocol and / or critical issues and related behavior to be followed in all situations

- If the dedicated nurse, during the daily inspection, realizes that the sacral MSP (in the patients of the experimental arm) has been removed without being positioned anymore, he provides to reposition it, marking in the CRF that the patient for that day remained without.

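### The primary comparison makes no use of the Braden score, which is known before allocation and not balanced by it; the crude test is valid, but a cheap gain in precision and protection against chance imbalance is forgone, mainly in the 280-patient area results.

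*Combined protocol and SAP*

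**What the plan says.** The primary endpoint is binary: "Incidence of PD to the sacrum of any category detected during the first 7 days of hospitalization". For such outcomes the Statistical analysis section states: "For all dichotomous variables the incidence, relative risk, relative risk reduction and number needed to treat will be calculated". The test is then named: "Fisher test will be used to evaluate the differences between the incidences of different outcomes between the experimental group and the control group". No regression, stratified or otherwise adjusted comparison appears anywhere in the document.

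The first inclusion criterion is "Patients at risk of developing PD measured with the Braden scale", with a cut-off of 16. The Method section puts the eligibility check and consent before the envelope is taken, so the score exists before allocation. Braden is also listed among the data collected. Its only planned use in the analysis is a subgroup split, "by risk level according to the Braden classification", running from severe to low.

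The Design section balances allocation by department and area, in blocks of 10, and not by Braden. The Sample size section requires the full size in each of the three areas: 280 per area, 840 in total.

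**The concern.** The protocol treats Braden as its measure of ulcer risk. The score defines who is at risk, it governs mattress use under standard preventive care, and it is graded into risk bands. A baseline value with that role would normally enter the main comparison. Here it is used only to cut the data into small subsets, which does nothing for the main estimate.

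Because Braden is not balanced, its distribution in the two arms is left to chance. If more high-risk patients fall in one arm of an area, the crude relative risk for that area combines the dressing effect with the difference in baseline risk. Without a prespecified adjustment, the investigators would then have to report that result as it stands or adjust after seeing the data. Post hoc adjustment is easier to challenge in a trial whose outcome assessors are not blinded.

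**Working it through.** **1. The plan's own figures.** From the Sample size section: 15.4% against 4.5%, alpha 0.05 (taken as two-sided), power 80%.

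n per arm = (1.960 + 0.842)² × [0.154 × 0.846 + 0.045 × 0.955] / (0.154 − 0.045)² = 114.5

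This gives 115 × 2 = 230, against the stated 228. For losses, 228 / (0.9 × 0.9) = 281.5, against the stated 280; 3 × 280 = 840. The figures reproduce. Full enrolment, 140 per arm per area, is used below.

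**2. Validity of the crude test.** By exact enumeration at 140 per arm, Fisher's true size at a 15.4% risk is about 3.3% and its power at the design rates is 84.1%.

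**3. Assumptions, none given in the documents.**
- Braden bands severe/high/moderate/low: 10/25/30/35% of patients, so 35% have a score of 12 or lower.
- Control risk by band, mild gradient: 27/20/15/9%. Average = 0.027 + 0.050 + 0.045 + 0.0315 = 15.4%.
- Control risk by band, steep gradient: 43/24/11/5%. Average = 0.043 + 0.060 + 0.033 + 0.0175 = 15.4%.
- Relative risk 4.5 / 15.4 = 0.292 in every band.

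**4. How often imbalance occurs.** The SD of the between-arm difference in the share with Braden 12 or lower is √(2 × 0.35 × 0.65 / n).
- One area, n = 140: 5.7 points. A gap of 8 points or more, in either direction, occurs in about 15% of areas by simulation; about 7.5% go against the dressing.
- At least one of three areas: 1 − 0.85³ = 39% in either direction; 1 − 0.925³ = 21% adverse.
- Pooled, n = 420: SD 3.3 points. A gap of 8 points or more occurs in about 1.5% of trials.

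**5. What imbalance does to the estimate.** Control risk at Braden 12 or lower against 13–16 is 22.0% against 11.8% (mild), or 29.4% against 7.8% (steep). An 8-point gap therefore shifts the crude difference by 0.08 × 10.2 = 0.8 points (mild) or 0.08 × 21.7 = 1.7 points (steep). Averaged over all adverse areas, where the gap is 8 points or more, the simulated shift with no true effect is 1.0 to 2.3 points. With Braden stratification it is about 0.

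**6. Power, one area, 60,000 simulated trials per scenario** (adjusted = Mantel-Haenszel over Braden bands):

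| | Mild | Steep |
|---|---|---|
| Adverse areas: Fisher | 78–79% | 72–73% |
| Adverse areas: chi-square | 83–84% | 78–79% |
| Adverse areas: adjusted | 88% | 90% |
| All trials: chi-square | 88% | 88% |
| All trials: adjusted minus chi-square | about 0.5 points | about 1.6 points |
| All trials: variance reduction, planned effect | 1% | 6% |
| All trials: variance reduction, no effect | 2% | 10% |

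Chi-square is the fair comparator. The rest of the gap from Fisher is Fisher's conservatism, which has nothing to do with Braden.

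**7. Cross-check with a different model.** A logistic likelihood-ratio test adjusted for Braden level and healed-ulcer history was simulated (1,500 trials per setting). Assumed odds ratios were 1.5, 2 or 2.5 per Braden level and 2, 3 or 4 for history, with history in 15–20% of patients. At 280 patients, power is 88–89% for chi-square and 89%, 91% or 92% adjusted, a gain of about 1–4 points from the two covariates together. The SD of log RR due to imbalance is 0.05–0.11, against a sampling SE of 0.44. That is (0.05/0.44)² = 1% to (0.11/0.44)² = 6% of the variance.

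**8. Events available for a model.** Per area: 140 × 0.154 + 140 × 0.045 = 21.6 + 6.3, about 28. Pooled: about 84. At 40 patients per centre and area there are 280 / 40 = 7 centres per area. A model with arm, Braden, history and six centre terms has 9 coefficients, or 28 / 9 ≈ 3 events each.

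**The case against.** The strongest case on the other side is that randomisation already makes this imbalance part of the random error that the test allows for. That stands. With no true effect and a gap of 8 points or more, crude Fisher rejects in about 3.9% (mild) or 5.0% (steep) of areas, so even these selected cases do not exceed the nominal level. The shift of 1.0–2.3 points compares with a sampling SD of about 4.3 points and a design effect of 10.9. In the equally frequent favourable cases, crude Fisher has 89–92% power, no less than the adjusted test.

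Three stronger readings are tempting, and the documents do not support them.

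- A reader might infer that the primary result is seriously exposed. The Statistical analysis section lists area as a subgroup analysis. The pooled comparison has 420 per arm, rarely meets a large imbalance, and has more than 99% power at the design rates.
- A reader might take Fisher's 72–79% against 88–90% as the cost of ignoring Braden. Those figures apply only to the 7.5% of areas with adverse imbalance, and they include Fisher's conservatism.
- A reader might treat healed sacral ulcer history, listed as "Pregressed (healed) PD to the sacred", as equally safe to adjust for. The entry criterion reads "with intact sacral skin and / or with signs of healing from previous sacral lesions", which requires a skin check but does not show that history is recorded before allocation. The Method section has the arm and the other variables of interest written down after the envelope is taken, and the CRF attachment is not available to settle the order.

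The objection does not show that leaving Braden out has any advantage. The score is already collected before allocation, and the adjusted analysis is at least as precise on average in every scenario tried.

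**Conclusion.** The point holds as an inexpensive improvement and not as a flaw in validity. The planned comparison omits a pre-allocation value that the protocol itself uses to grade risk. The consequence is a small average loss of precision, and conditional bias in an area where Braden happens to be uneven. There is no inflation of type I error, and the pooled comparison is barely affected.

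The probability of imbalance depends on the assumed 35% share with Braden 12 or lower. The power and variance figures depend also on the assumed gradients and a constant relative risk. A flatter gradient would shrink the benefit towards zero; a steeper one would enlarge it. Evaluable numbers below 140 per arm would make imbalance somewhat more frequent.

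**What to change.** Prespecify a Braden-adjusted primary analysis of sacral pressure ulcer:

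- **Pooled comparison:** a logistic model with arm, Braden score and area (centre as well, if events allow), standardised over the sample to give an adjusted relative risk and risk difference with 95% confidence intervals. Arm, one Braden term and two area terms make 4 coefficients for about 84 events, or 21 each.
- **Within each area:** adjust for Braden only, with one linear term or by Mantel-Haenszel over the Braden bands. About 28 events cannot carry centre terms as well.
- **Healed sacral ulcer history:** add it only if the CRF shows that it is recorded before the envelope is opened, and events allow.
- **Crude Fisher test and crude relative risk:** keep as supportive.

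The cost is one paragraph in the Statistical analysis section and an amendment to the Ethics Committee, which the protocol requires for a change of analysis. Braden needs no new data and no further patients are needed. The downside is that the model must be fixed in advance and kept small, with a stated fallback, such as Mantel-Haenszel, if events are sparse.

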- At discharge or on the appearance of pressure lesion on the sacrum ≥ 2nd category, the CRF is closed and the patient ends the study. If the patient has developed PD the treatment of the lesion will be performed according to the hospital policy.
- The medication will be removed, however, no later than the first 7 days of admission after which the patient ends the study.

Study exit criteria

- Withdrawal of informed consent before randomization
- Not randomized within 24 hours of admission

Conclusion of the study in the single recruited subject

- Withdrawal of consent after randomization
- The appearance of irritation to the skin caused by the dressing. The dressing is removed, reported in CRF and irritation treated as per hospital policy.
- At the request of the patient due to discomfort due to preventive medication.
- On discharge / death / transfer to ward not involved in the study before the 7th day after randomization
- After 7 days from randomization in the absence of PD to the sacrum
- The appearance of pressure injury to the sacrum higher than the first category

Sample size

From a randomized monocentric study of at-risk patients with a hip fracture where polyurethane foams were used in prevention, the incidence in the experimental group was 4.5% while in the control group of 15.4%. Similar deltas had also been identified in other trials in intensive care patients. Assuming similar results in the population subject of the present study and taking into account an alpha error of 0.05 and a beta error of 20%, it is necessary to enroll at least 228 patients at risk. In order to allow analyzes by subgroup (see the "statistical analysis" section) the sample size must be guaranteed for each area (medical, surgical, intensive).

Taking into account also a possible loss at the follow-up of 10% and also assuming a 10% withdrawal rate, the necessary sample will be 280 patients per area and therefore a total of 840 patients (420 per arm). Each hospital involved will enroll 40 patients per area involved in that specific hospital.

Randomization

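### Each area is sized for its own analysis, but the plan has no test of whether the dressing's effect differs between areas

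*Combined protocol and SAP*

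**What the plan says.** The Sample size section derives a requirement of 228 patients from incidences of 15.4% (control) and 4.5% (dressing), with alpha 0.05 and beta 20%. It then applies that requirement to each of the three areas, giving as its reason: "In order to allow analyzes by subgroup". After allowance for losses and withdrawals, the target is "280 patients per area and therefore a total of 840 patients".

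The Statistical analysis section lists subgroup analyses by area (three levels), Braden band (four) and origin (two). For incidences it names one test: "Fisher test will be used to evaluate the differences between the incidences of different outcomes" in the two arms. It also asks for the incidence, relative risk, relative risk reduction and number needed to treat for dichotomous variables. It closes with: "For all tests, a p <0.05 will be considered significant".

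The protocol contains no interaction or heterogeneity test and no exploratory label. It does not state confidence intervals, or that relative risks will be given by area.

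**The concern.** Sizing each area for the between-arm comparison, and naming only Fisher's test at p<0.05, leads most naturally to three stand-alone verdicts, one per area. Three such verdicts do not compare the areas. One area can reach p<0.05 and another miss it by chance alone, although the dressing works equally well in both.

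This matters because the area analyses determine the size of the trial. The Background also faults earlier trials because "the populations investigated are very specific, limiting the generalizability of results". Readers will therefore want to know whether the effect carries across medical, surgical and intensive care, and the plan gives no method that addresses this.

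**Working it through.** **Inputs.** From Sample size: 15.4% and 4.5%, alpha 0.05, power 80%, 228 patients before and 280 after inflation in each area, with 10% loss and 10% withdrawal. From Design: 1:1 allocation. From Statistical analysis: Fisher's exact test, p<0.05. Assumptions: two-sided testing, which is not stated, and the same two rates in every area.

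**1. The plan's own figure.** The unpooled normal approximation gives n per arm = (1.960 + 0.842)² × [0.154 × 0.846 + 0.045 × 0.955] / (0.154 − 0.045)² = 7.849 × 0.17326 / 0.011881 = 114.5. That is about 229 to 230 in total, against 228 stated. Inflation gives 228 / (0.9 × 0.9) = 281.5, against 280 stated, and 3 × 280 = 840. The plan's figures are reproduced closely. Each area would have between 114 per arm (planned losses occur) and 140 per arm (everyone evaluable).

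**2. Fisher power in one area**, by full enumeration of both binomials: 0.7385 at 114 per arm and 0.8409 at 140.

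**3. Three independent areas with one identical effect.** With power p in each area, the chance of a mixed result (one or two of three significant) is 1 − p³ − (1 − p)³.

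| Areas at p<0.05 | 114 per arm | 140 per arm |
|---|---|---|
| All three | 0.403 | 0.595 |
| Two | 0.428 | 0.337 |
| One | 0.151 | 0.064 |
| None | 0.018 | 0.004 |
| **Mixed (one or two)** | **0.579** | **0.401** |

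At exactly 80% power the mixed chance is 1 − 0.512 − 0.008 = 0.480. With a normal-approximation test instead of Fisher (power 0.789 and 0.865) it would be 0.500 and 0.349.

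**4. What an interaction test would do.** A likelihood-ratio test of treatment by area in a logistic model (2 degrees of freedom, 200,000 simulated trials per setting) gives:

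| Setting | 114 per arm | 140 per arm |
|---|---|---|
| Identical effect: rejects | 0.062 | 0.057 |
| Identical effect, mixed verdict: test non-significant | 0.907 | 0.887 |
| Third area has no effect: rejects | 0.666 | 0.757 |
| Third area has RR 0.6: rejects | 0.228 | 0.269 |

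**5. Pooled comparison.** Fisher power at the design rates is 0.9980 with 342 per arm (3 × 114) and 0.9997 with 420 per arm (3 × 140).

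**6. Sensitivity to the control rate.** The Background cites incidences of 6.5% in medical and 13.1% in intensive care patients. Take these as control rates, assume 15.4% for surgery, and keep the relative risk at 0.045 / 0.154 = 0.29. Fisher power at 114 per arm is then 0.285 (medical), 0.739 (surgical) and 0.651 (intensive). The mixed chance is 1 − 0.285 × 0.739 × 0.651 − 0.715 × 0.261 × 0.349 = 0.80. At 140 per arm the powers are 0.363, 0.841 and 0.757, and the mixed chance is 0.74.

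**The case against.** The strongest reply is that the harm depends on a misreading that the plan never announces. A reader might infer that the trialists will treat differing p-values as differing effects. The protocol does not say so, and a difference between areas is not among its stated aims. Whether the dressing works in a given area is a legitimate question, the areas are pre-specified, and randomization is organised by area. Any trial with three strata at 80% power would show a mixed result 48% of the time under one effect. All of this stands. It does not turn separate p-values into a comparison between areas.

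The planned relative risks also help. In simulations of the same scenario, all three area relative risks favoured the dressing in 98.6% (114 per arm) and 99.2% (140 per arm) of trials with a mixed verdict. This mitigation is real but partial, because neither confidence intervals nor relative risks by area are stated.

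A reader might also infer separate Fisher tests within Braden bands and origin groups. For area that reading follows from the sizing; for the other two it is inference only, and no figure here concerns them.

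Finally, a reader might infer that the missing error control across areas is itself a defect. With 15.4% in both arms everywhere, Fisher's actual size is about 0.033 per area, so the chance of at least one significant area is 1 − (1 − 0.033)³, about 10%. It is about 2% if area results are read only alongside a significant pooled result, a condition the plan does not state. Whether stand-alone area claims need adjustment is debatable, and the documents do not settle it.

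**Conclusion.** The point holds for area. The plan sizes three areas for separate analysis and names no method for judging whether the effect differs between them. Under one identical effect, the separate tests would disagree in about 40% to 58% of trials. That range rests on two-sided Fisher tests, on 15.4% against 4.5% in every area, and on 114 to 140 evaluable patients per arm. It is not a bound: with the lower control rates in step 6 it would be 74% to 80%.

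The pooled primary comparison is unaffected. This is a cheap and worthwhile improvement in how area results are analysed and reported, not a threat to the trial's main conclusion.

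**What to change.** In the Statistical analysis section:

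- State that the pooled 7-day comparison is the confirmatory test.
- For area, add one treatment-by-area interaction test: a likelihood-ratio test in a logistic model with treatment, area and their product. It can still be computed when an area has no events in one arm.
- Report its p-value beside each area's relative risk with 95% confidence interval.
- Base no claim of a differing effect on within-area p-values, and do not read a non-significant interaction as proof of consistency.
- Treat Braden band and origin the same way and label them exploratory.

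Error control across the three areas is optional. If stand-alone area claims are wanted, the plan could declare them in advance and say whether the error is controlled, for example by Holm.

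The cost is a few sentences, three models and the Ethics Committee amendment that the protocol requires for changes to the statistical analysis; no extra patients are needed. The drawbacks should be stated openly. Power is limited: about 67% to 76% if one area has no effect, and about 23% to 27% if that area's relative risk is 0.6. The size is about 6% rather than 5%. The test works on the odds-ratio scale, while the plan reports relative risks.
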